### **18.3 Revisions to the Protocol**

Roswell Park may make such changes to the protocol as it deems necessary for safety reasons or as may be required by the U.S. FDA or other regulatory agencies. Revisions will be submitted to the IRB/ERC for written approval before implementation.

### **18.4 Termination of the Study**

It is agreed that, for reasonable cause, either the Roswell Park Investigators or the Sponsor, may terminate this study, provided a written notice is submitted within the time period provided for in the Clinical Trial Agreement. In addition, Roswell Park may terminate the study at any time upon immediate notice if it believes termination is necessary for the safety of participants enrolled in the study.

## **19 STATISTICAL PLAN**

### **19.1 Study Design/Endpoints**

This is prospective Phase I/IIa trial basket trial of i.v. rintatolimod administered with or without i.v. IFN $\alpha$  (INTRON $\circledR$  A) in two cohorts of patients: Main Cohort and Expansion Cohort. Only Main Cohort subjects will participate in the Phase I 3+3 portion of this study. The Expansion

Roswell Park Protocol No.: I-659920

Cohort will consist of rintatolimod without IFN $\alpha$ . Neither cohort is randomized. The kinetics of nasopharyngeal viral load will be assessed based on baseline values and on treatment and EOT values. In the Expansion Cohort, the kinetics of nasopharyngeal viral load will be compared with historical controls consisting of Roswell Park patients with COVID-19 of varying severity. All patients will receive best available standard of care in addition to study drug regimens.

**Phase I.** The Phase I component of the protocol consists of a 3+3 design with four dose levels of IFN $\alpha$  (0, 5 MU/M, 10 MU/M and 20 MU/M ) and fixed dose rintatolimod (200 mg per day) administered on Days 1 and 3. The sample size for the Phase I trial may range from n=3 to 24.

### **Primary Endpoint**

- The primary safety endpoint is the frequency of grade 3 or 4 AEs considered to be possibly, probably, or definitely related to the treatment regimen.

**Phase IIa.** The Phase IIa component of the trial is designed to be a single arm trial of IFN $\alpha$  (at MTD, if reached, otherwise at 20 MU/M) + rintatolimod along with the best available standard of care. Using each patient's baseline nasopharyngeal viral load, we will evaluate to what extent the study regimen reduces viral load relative historical institutional benchmarks. The sample size will be n=10.

### **Primary Endpoint**

- Evaluate kinetics of viral load expressed as Ct values in nasopharyngeal swab samples over time measured at baseline (day 0), Days 3 (last day of treatment), 7, and 14 (40). The primary endpoint will be the area under the Ct curve (AUC).

The primary Phase IIa safety endpoint is the frequency of grade 3 or 4 AEs considered to be probably or definitely related to the treatment regimen.

### **Secondary Endpoints**

- Clinical efficacy will be assessed by the frequency of these complications: (i) progression of infection requiring hospitalization; (ii) respiratory failure requiring mechanical ventilation; (iii) death within 30 days and (iv) Time to a Ct value of non-detectable.

### **Correlative Endpoints**

- Determine the kinetics of changes of the immune subsets and circulating inflammatory mediators (including CRP, cytokines, chemokines, interferons) in peripheral blood in the course of treatment at baseline (Day 0), Days 3, 7, and 14. Plasma and PBMCs will be cryopreserved for future exploratory studies, including the assessment of intracellular signaling and TCR and BCR repertoires as correlates of response to the study regimen.
- Induction of known mediators of antiviral immunity that include (myxovirus resistance gene, MxA; protein Kinase R (PKR); oligoadenylate synthetase-2 (OAS2); RNase-L, IFN-stimulated gene-15 (ISG15); IFN-induced proteins with tetratricopeptide repeats (IFIT1) and IFN-inducible transmembrane protein 3 (IFITM3), TLR3, RIG-I, MDA5, IRF3, IRF7, in nasopharyngeal swabs material and blood cells of patients on all tiers of treatment. Expression of ACE2 (receptor for SARS-CoV-2 entry) and potentially other genes involved in SARS-CoV-2 infection will be tested in nasopharyngeal samples.

Roswell Park Protocol No.: I-659920

All subjects meeting the eligibility criteria who signed a consent form and receive rintatolimod control will be considered evaluable for efficacy analysis. Safety analysis will be performed on all patients who have signed a consent form and received at least one dose of study medication.

The primary efficacy analysis of the Phase IIa component of the study will be on the intention to treat (ITT) population, which will include all patients who have signed a consent form and undergone randomization, according to the treatment group to which they were allocated.

All data collected will be summarized and presented. Continuous variables will be described as the mean, median, standard deviation, and range of the observations. Categorical data will be described with contingency tables including frequency and percentage. Individual patient listings will be generated and presented.

Statistical descriptions and analyses will be carried out using SAS statistical analysis software version 9.4 or higher (SAS Institute, Inc., Cary, North Carolina, USA).

## 19.2 Proposed Data Analysis

### 19.2.1 Safety

#### SAFETY RUN-IN DESIGN

We will use a 3+3 dose escalation scheme in order to determine the safe dose to utilize in our efficacy analysis. The 3+3 design will consider four dose levels of IFN $\alpha$  (0, 5 MU/M $^2$ , 10 MU/M $^2$  and 20 MU/M $^2$ ) and fixed dose rintatolimod (200 mg per day) administered on Days 1 and 3.

For each cohort, the given dose level will start with three patients, with three patients added to any dose level if we observe 1 out of 3 DLTs. The patients in each cohort will be staggered, so that the first patient in each cohort will have received treatment on Days 1 and 3 before the following patient(s) are enrolled in that cohort. If 2 out of 3 to 6 subjects have a DLT we will not proceed to the next dose level.

### 19.2.2 Efficacy

In order to compare the AUC between rintatolimod versus historical institutional benchmarks we will use the highly efficient approach proposed by Chandrasekhar et al (48). Ct values measured at baseline (Day 0), Days 3, 7 and 14 will be used to measure the AUC using a standard trapezoidal rule where the AUC for the  $i$ th subject in group  $k$  ( $k=1$  for rintatolimod and  $k=2$  for control) as  $AUC_{jk} = \sum_{i=1}^m c_j Y_{ijk}$  where  $t_1 = 0, t_2 = 3, t_3 = 7, t_4 = 14, t_5 = 30$ ,  $m = 5$ , the  $Y_{ijk}$ 's denote the corresponding Ct values per subject at the respective time points and

$$c_j = \begin{cases} \frac{t_{j+1} - t_j}{2}, & j = 1 \\ \frac{t_j - t_{j-1}}{2}, & j = m \\ \frac{t_{j+1} - t_{j-1}}{2}, & \text{otherwise} \end{cases}$$

If a Ct value is  $>40$  it will be considered right censored for the purpose of this analysis, which corresponds to a non-detectable level. We can re-express this formulation using a linear mixed model with details given exactly as in Chandrasekhar et al. (48). A large AUC value for a respective subject is a measure of treatment efficacy as compared to a subject with a lower AUC

Roswell Park Protocol No.: I-659920

value. The primary test of efficacy will be H0:  $AUC=130$  (log2 copies) x day versus H1:  $AUC>130$  (log2 copies) x day.

The secondary clinical efficacy endpoints of (i) progression of infection requiring hospitalization in patients who were not inpatients at study entry; (ii) respiratory failure requiring mechanical ventilation; and (iii) death within 30 days will be compared using Fisher's exact test. Time to a Ct value of non-detectable will be examined using an exact discrete time-to-event Cox model. The analysis of correlative endpoints will be primarily descriptive and graphical in nature.

The primary test of efficacy will be one-sided and tested at level alpha=0.05. All additional tests will be two-sided and tested at level alpha=0.05.

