## **4 LOCAL AND STUDY-WIDE NUMBER OF SUBJECTS**

Maximum number of Roswell Park subjects: The anticipated number of subjects required for the main portion of the study is 44. All patients must have cancer and need not be established Roswell Park patients. The modification of the protocol triggered by the observed high effectiveness of the treatment in the first patient who received rintatolimod alone will include additional 20 cancer patients (Expansion Cohort).

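### The primary AUC test is written for rintatolimod, but its endpoint and n=10 belong to the IFN-alpha plus rintatolimod arm, and the Expansion Cohort's comparison with history has no stated role

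*Combined protocol and SAP*

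**What the plan says.** Section 19.2.2 opens its efficacy method with "In order to compare the AUC between rintatolimod versus historical institutional benchmarks". It labels k=1 as rintatolimod and k=2 as control, and tests H0: AUC=130 against AUC>130, one-sided at 0.05. All additional tests are two-sided at 0.05.

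The Phase IIa paragraph of Section 19.1 says "The Phase IIa component of the trial is designed to be a single arm trial of" IFN-alpha (at the MTD, otherwise at 20 MU/M²) plus "rintatolimod along with the best available standard of care", and "The sample size will be n=10". The AUC of Ct is listed as the primary endpoint of that component. Section 19.3 sizes the test at n=10.

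The opening of Section 19.1 says of the cohort treated without IFN-alpha: "In the Expansion Cohort, the kinetics of nasopharyngeal viral load will be compared with historical controls". Section 4.1 caps that cohort at 20.

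Two analysis sets follow the correlative endpoints in Section 19.1. The first says that eligible, consented subjects who "receive rintatolimod control will be considered evaluable for efficacy analysis". The second, for the primary Phase IIa analysis, is an ITT set of consented patients who were randomized. Section 19.4 says the trial is not randomized.

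**The concern.** The regimen named in the primary method is not the regimen of the arm for which the test was sized. A programmer working from Section 19.2.2 alone could select the Expansion Cohort, or everyone who received rintatolimod. One working from the Phase IIa paragraph would select the ten combination patients.

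These groups differ in more than IFN-alpha. The Expansion Cohort admits more severe COVID-19 and allogeneic transplant recipients (Section 3.3) and allows up to 12 infusions (Section 10). The Main Cohort excludes both kinds of patient and plans two doses. Section 2.6 reports viral load persisting for weeks in some transplant recipients, so a mixed mean could move in either direction.

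A positive result would then not say which regimen it supports. The choice of cohort would also stay open after data are seen, in a small non-randomized study tested against a fixed benchmark. In addition, the Expansion comparison has no hypothesis, alpha share, place in an order or descriptive label, so it could become a second route to a claim of benefit.

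**Working it through.** **Step 1. Which patients does each place select?**

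| Place | Group selected |
|---|---|
| 19.2.2, k=1 | rintatolimod; cohort and IFN-alpha dose not stated |
| 19.1, Phase IIa and its primary endpoint | IFN-alpha plus rintatolimod, n=10 |
| 19.3 | n=10, H0: AUC=130; regimen not named |
| 19.1, opening | Expansion Cohort, rintatolimod without IFN-alpha, up to 20, compared with history |
| 19.1, evaluable set | anyone eligible and consented who receives rintatolimod (the wording is garbled); not limited by cohort or dose |
| 19.1, Phase IIa ITT set | randomized patients; none, given 19.4 |

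Taken literally, the evaluable set spans up to 24 Phase I patients, 10 Phase IIa patients and up to 20 Expansion patients, while the ITT set is empty. Neither identifies the ten patients for whom the test was sized.

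**Step 2. The plan's own figures.** The nominal error rate is 5%, and it holds if H0 is tested once in one named group.

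The stated power of 0.80 (130 versus 144, n=10) does not reproduce from Section 19.3's inputs. The trapezoid weights for Days 0, 3, 7 and 14 are 1.5, 3.5, 5.5 and 3.5. The SDs are 6.5 at baseline and 4.5 afterwards, so weight × SD is 9.75, 15.75, 24.75 and 15.75, with sum 66.0 and sum of squares 1203.75. With compound symmetry and rho=0.3:

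Var(AUC) = 0.7 × 1203.75 + 0.3 × 66.0² = 842.6 + 1306.8 = 2149.4, so SD = 46.4.

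Power = Φ(14 × √10 / 46.4 − 1.645) = Φ(−0.69) = 24.5%.

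That is a separate problem, and the present point does not depend on it.

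**Step 3. Chance of at least one false claim of benefit.** Inputs from Section 19.2.2: primary test one-sided 0.05; additional tests two-sided 0.05, so 0.025 in the direction of benefit. Assumptions: the Phase IIa and Expansion patients are different people, each group is compared with a fixed benchmark (so the tests are independent), and neither regimen has an effect.

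- Expansion comparison descriptive: 5%.
- Expansion tested two-sided at 0.05: 1 − 0.95 × 0.975 = 0.0738, or 7.4%.
- Expansion tested one-sided at 0.05: 1 − 0.95² = 0.0975, or about 9.8%.

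If both cohorts share a historical mean estimated from 20 patients (an assumed number) instead of a fixed 130, simulation puts the last figure at about 9.0%. Whatever the dependence, two 5% tests cannot exceed 10%.

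**The case against.** The strongest reply is that the documents largely assign the test already. Section 19.1 lists AUC as primary under Phase IIa and speaks of the primary efficacy analysis of that component. Section 19.2.1 says escalation finds the dose for the efficacy analysis, and only IFN-alpha is escalated. Section 19.3 uses n=10. On this reading, rintatolimod in Section 19.2.2 is shorthand for the combination. This stands as the most sensible reading, but it does not repair a group definition that names another regimen, or an ITT set that no patient can enter.

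Three stronger conclusions are tempting and are not supported:

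- A reader might infer that the stated alpha is exceeded. No passage calls the Expansion comparison primary or describes it as a formal test. The primary test's own error rate is 5% in any case, and unadjusted secondary tests are common in small Phase I/IIa studies.
- A reader might infer a planned pooled test from the evaluability sentence. That sentence says who can be evaluated; nothing proposes combining cohorts.
- Section 4 says the Expansion Cohort was "triggered by the observed high effectiveness of the treatment in the first patient who received rintatolimod alone", and a reader might infer that this patient's result is reused to test the idea it suggested. Sections 9 and 10 place that patient at the lowest tier of the Main Cohort escalation, and the Expansion Cohort is an additional 20. The patient is therefore in neither the Phase IIa ten nor the Expansion twenty, so no bias should be claimed and no exclusion is needed.

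**Conclusion.** The point holds as a contradiction in definitions. The group named in Section 19.2.2 does not match the arm to which the primary endpoint and sample size belong, and the analysis sets cannot resolve the mismatch. The likely intent is one test in the Phase IIa combination arm, but the text permits another or a mixed cohort.

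The effect on error is conditional: 5% if the Expansion comparison is descriptive, 7.4% if it is tested under the plan's own two-sided rule, and at most about 9.8% if it is tested one-sided at 5%. The last two figures assume independent groups, a fixed benchmark and no effect of either regimen. The 7.4% figure should lead, because no passage states a second one-sided test. The wording should be settled before the data are analysed.

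**What to change.** - In Section 19.2.2, define k=1 as the Phase IIa patients who receive IFN-alpha plus rintatolimod, and state that H0: AUC=130 is tested once, in that group.
- In Section 19.1, replace the ITT definition based on randomization with all enrolled Phase IIa patients.
- State that the Expansion Cohort comparison with historical controls is a separate secondary analysis, reported as an estimate with a two-sided 95% CI, with no efficacy claim from it alone.
- State that cohorts are not pooled for the primary efficacy test.

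This changes wording only and adds no patients or visits. The cost is that the Expansion Cohort cannot support a significance claim of its own. In return, the error rate of the efficacy claim based on AUC stays at 5% and the result belongs to one identified regimen.

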## 7 STUDY TIMELINES

Main Cohort: A maximum of 44 evaluable participants will be enrolled to the study over up to 36-months. Patients will be followed until Day 30 after initiation of the study regimen.

Expansion Cohort: A maximum of 20 evaluable participants will be enrolled to the study over up to 36-months. Patients will be followed until Day 30 after initiation of the study regimen.

Enrollment in the Main Cohort and Expansion Cohort will be done concurrently. If a patient is eligible for enrollment in both the Main and Expansion Cohort and is willing to be enrolled in either cohort, priority will be given to the Main Cohort.

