### **11.2 Follow-up Visits on Days 7 ( $\pm$ 1 day) and 14 ( $\pm$ 3 days)**

- Recording of concomitant medications
- Recording of Adverse Events
- Targeted physical exam
  - Lung auscultation and Vital Signs
- ECOG Performance Status
- Hematology
- Chemistry
- Blood (30cc) for correlative studies
- Nasopharyngeal swabs for viral quantification by quantitative PCR

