#### **11.4 Nasopharyngeal swabs**

Nasopharyngeal swabs will be taken for viral quantification by quantitative PCR on:

- Screening: If a potential study participant has already been identified as COVID-19-positive from an outside testing facility, as per current institutional protocol, a nasopharyngeal swab will be obtained for quantitative PCR. Study drug therapy will be initiated within 3 days of screening, including on the same day of screening.
- Each day of treatment (Day 1 and Day 3 (+ 1 day)).
- Follow-up Visits on Days 7 and 14

Testing for SARS-CoV-2 will be done upfront and residual samples will be tested for baseline viral load. If there's a problem in supplies, repeat sampling at the indicated time points may not be feasible and will not be considered a protocol deviation.

All samples will be transported to the Molecular Diagnostics facility (Attn: [name]) The screening samples will be tested for SARS-CoV-2 as per current institutional protocol; The residual sample left over from clinical testing, as well as from subsequent testing, will be processed by the Molecular Diagnostics facility and the resulting research analytes will be transported to the [name] laboratory for storage and analysis ([name]).

Any remaining RNA may be also analyzed for the markers of antiviral immunity described in the blood correlative studies.

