## Appendix F

### Study Calendar (Main Cohort)

Baseline and/or Screening assessments must be performed within 3 days prior to the first dose of investigational product unless otherwise stated. Therapy may begin on the same day as screening. *If screening and day 1 are completed on the same day, then assessments required on both days may be done only once\**. Any results falling outside of the reference ranges may be repeated at the discretion of the investigator.

\*If screening and day 1 occur on the same day, correlative blood draw and nasopharyngeal swab collection will be as follows:

Correlative blood draw: In the case when day one of treatment is the same as the screening day, only two blood draws (30 mL each time) are needed for the correlative studies on that day: Before the start of treatment and within 1 hour after the end of the combined infusion (i.e., collect one pre-dose sample and one sample within one hour after end of rintatolimod IV, if screening and Day 1 are the same day).

Nasopharyngeal swabs: In the case when day one of treatment is the same as the screening day, only one nasopharyngeal swab (pre-dose) is required.

Evaluation	Screening and Informed Consent	Day 1	Day 3 (+ 1 day)	Day 7 (± 1 day) and Day 14 (± 3 days) 
Written Informed Consent prior to any Screening Procedures	X			
Recording of Concomitant Medications		X	X	X
Recording of Adverse Events		X	X	X
Survival Follow-up (through Day 14)		X	X	X
Clinical Assessments				
Medical & Surgical History		X		

Evaluation	Screening and Informed Consent	Day 1	Day 3 (+ 1 day)	Day 7 (± 1 day) and Day 14 (± 3 days)
Physical Exam including vital signs 	X	X	X	X
ECOG Performance Status	X	X	X	X
Laboratory Procedures				
CBC with diff	X	X	X	X
CMP	X	X	X	X
Serum hCG in women of child-bearing potential	X			
ABG	X			
Blood (30cc) for immunologic studies 	X	X (prior to treatment) and X (within 1hr after end of infusion treatment)	X (prior to treatment) and X (within 1hr after end of infusion treatment)	X 2a
Nasopharyngeal Swab (as required and based on availability)	X	X	X	X
Imaging/ Other Procedures				
12-Lead ECG	X			
CXR or CT scan 	X			

Evaluation	Screening and Informed Consent	Day 1	Day 3 (+ 1 day)	Day 7 (± 1 day) and Day 14 (± 3 days)
Clinical evaluation of endpoints 	X	X	X	X

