**Study Calendar (Expansion Basket: Rintatolimod)**

Evaluation	Screening and Informed Consent	Day 1	Day 3 (or Day 4) 	Day 7 ( $\pm$ 1 day) and Day 14 ( $\pm$ 3 days) and Day 30 ( $\pm$ 3 days) 
Written Informed Consent prior to any Screening Procedures	X			
Recording of Concomitant Medications		X	X	X
Recording of Adverse Events		X	X	X
Survival Follow-up (through Day 14)		X	X	X
Clinical Assessments				
Medical & Surgical History		X		
Physical Exam including vital signs 	X	X	X	X
ECOG Performance Status	X	X	X	X
Laboratory Procedures				
CBC with diff	X	X	X	X
CMP	X	X	X	X
Serum hCG in women of child-bearing potential	X			

Evaluation	Screening and Informed Consent	Day 1	Day 3 (or Day 4)	Day 7 (<math>\pm</math> 1 day) and Day 14 (<math>\pm</math> 3 days) and Day 30 (<math>\pm</math> 3 days)
ABG	X			
Blood (30cc) for immunologic studies 	X	X (prior to treatment) and X (within 1hr after end of infusion treatment)	X	X 2a
Nasopharyngeal Swab (as required and based on availability)	X	X	X	X
Imaging/ Other Procedures				
12-Lead ECG	X			
CXR or CT scan 	X			
Clinical evaluation of endpoints 	X	X	X	X
Study Drug Administration				
Rintatolimod Administration + best available SOC		X	X	X 

1. Hospitalization in patients who were not inpatients at study entry; respiratory failure requiring mechanical ventilation; 15-day survival.
2. Blood (30cc) for correlative studies: On Day 1 prior to treatment and within 1 hour after end of infusion treatment (two draws on Day 1). Note: The treatment begins with IV rintatolimod, with the correlative blood draw within 1 hour following IV rintatolimod as indicated above. Refer to Section 11.4.

2a: Follow-up visits- NOTE: In the event patient cannot tolerate treatment, then blood (30cc) for correlatives will be collected at time that the patient recovers from toxicities (ideally within 1 week of the infusion).

3. Physical exam will be limited to vitals and auscultation of lungs. Vital signs (temperature, heart rate, respiratory rate, blood pressure,  $\text{SaO}_2$ ), body weight, and height: Height collected at baseline only.
4. NOTE: If a chest CT is ordered as standard of care prior to starting treatment, a chest x-ray is not required.

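### The primary AUC formula in 19.2.2 runs to Day 30, the endpoint and Phase IIa swabs stop at Day 14, and the null value of 130 fits neither window

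*Combined protocol and SAP*

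**What the plan says.** Section 19.2.2 gives two sets of time points for one statistic. The sentence introducing the trapezoidal rule says "Ct values measured at baseline (Day 0), Days 3, 7 and 14 will be used to measure the AUC". The formula that follows sets m = 5 and "t_1 = 0, t_2 = 3, t_3 = 7, t_4 = 14, t_5 = 30".

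The other Phase IIa text supports four points:

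- Section 19.1 defines the Phase IIa primary endpoint as the AUC of Ct "measured at baseline (day 0), Days 3 (last day of treatment), 7, and 14".
- Section 11.4 lists the post-treatment swabs as "Follow-up Visits on Days 7 and 14", and 11.2 names the same two visits.
- The last column of the Main Cohort calendar (Appendix F) is "Day 7 (± 1 day) and Day 14 (± 3 days"). Section 4.1 places the ten Phase IIa patients in this cohort.

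Day 30 appears in two other places. The Expansion Cohort calendar has a Day 30 visit with the swab row marked. Section 7 says of both cohorts "Patients will be followed until Day 30 after initiation of the study regimen", but names no swab.

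The primary test (19.2.2) is one-sided, AUC = 130 against AUC > 130. Section 19.3 says 130 comes from pilot data and claims power 0.80 to detect 144 with n = 10. Neither section gives the window over which 130 and 144 were calculated.

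**The concern.** A trapezoidal AUC depends on its time points. Moving the last point from Day 14 to Day 30 adds a term, more than triples the weight on Day 14 (3.5 to 11.5), and changes the mean, the variance and the power. These are two different endpoints.

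The trial has one arm, so the fixed null value does the work of a control group. It is a fair benchmark only if it was built on the same days and weights as the patients' AUC. If it was not, rejecting the null says nothing about treatment. The formula for the primary test does not match the endpoint it is meant to test, and the benchmark and power cannot be tied to either version.

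**Working it through.** **Inputs.** From 19.3: baseline Ct mean 24.1 and SD 6.5; SD about 4.5 after baseline; between-time correlation ρ = 0.3 with compound symmetry; n = 10; one-sided α = 0.05; null 130; alternative 144, so a difference of 14. The weights c_j come from the rule in 19.2.2.

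**The plan's own figure.** Power 0.80 for a difference of 14 with n = 10 implies an AUC SD of 14√10 / (1.645 + 0.842) = 17.8 by the normal approximation, or 16.4 by the noncentral t.

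**Weights.**

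- Days 0, 3, 7, 14: c = (1.5, 3.5, 5.5, 3.5), sum 14 days.
- Days 0, 3, 7, 14, 30: c = (1.5, 3.5, 5.5, 11.5, 8), sum 30 days.

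In the five-point version 16 of 30 days (53%) lie after the last scheduled Phase IIa swab, and Days 14 and 30 together carry 19.5/30 = 65% of the weight.

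**SD of the AUC.** Under compound symmetry, Var = 0.7 Σ(c_j s_j)² + 0.3 (Σ c_j s_j)².

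- Days 0–14: c_j s_j = (9.75, 15.75, 24.75, 15.75); sum 66; sum of squares 1203.75. Var = 842.6 + 1306.8 = 2149.4; SD = 46.4.
- Days 0–30: c_j s_j = (9.75, 15.75, 24.75, 51.75, 36); sum 138; sum of squares 4929.75. Var = 3450.8 + 5713.2 = 9164.0; SD = 95.7. This assumes SD 4.5 and ρ = 0.3 still hold at Day 30, which 19.3 does not say. A Day 30 SD of 3 to 6 gives 87.8 to 104.4, with ρ kept at 0.3.

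**Power and detectable difference** (one-sample t test, noncentral t):

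| | Days 0–14 | Days 0–30 |
|---|---|---|
| SD of AUC | 46.4 | 95.7 |
| Power for a difference of 14, n = 10 | 0.22 | 0.11 |
| Difference detectable at 80% power, n = 10 | 39.5 | 81.6 |
| Patients needed for a difference of 14 at 80% power | about 70 | about 291 |

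The normal approximation gives power 0.25 and 0.12.

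**Does 130 fit either window?** An AUC of 130 is a mean Ct of 130/14 = 9.3 or 130/30 = 4.3. The pilot baseline mean is 24.1 and 19.3 says Ct rose afterwards. A Ct flat at 24.1 gives 24.1 × 14 = 337 or 24.1 × 30 = 723.

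**Consequence for the test.** Take ten patients whose Ct stays at 24.1. The expected t statistic against 130 is roughly (337 − 130)/(46.4/√10) = 14.1 for Days 0–14, or (723 − 130)/(95.7/√10) = 19.6 for Days 0–30. The one-sided critical value on 9 degrees of freedom is 1.83. The null is rejected with probability close to 1 in either case.

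**The case against.** The strongest counter-argument is that the window error and the benchmark error are separate faults. Power of 0.22 and a mean Ct of 9.3 arise under the four-point version too, so removing Day 30 cures neither. The window alone accounts for SD 46.4 versus 95.7, power 0.22 versus 0.11, and the 53% of the interval without a scheduled swab. Most of the text says four points, and an analyst would probably default to that. This stands as a matter of attribution. It is also why correcting m is not enough.

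Day 30 may not be a slip. An unweighted sum of five Ct values, with the SDs and ρ of 19.3, has SD 16.3 and power 0.804 at n = 10, and 130/5 = 26.0 lies near the baseline mean. The sample size may have been built on five values. The plan describes no such statistic, so this is inference. If it is what happened, the benchmark was computed on a different quantity from the trapezoidal AUC being tested, which confirms the mismatch.

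The five-point formula could be meant for the Expansion Cohort, which has a Day 30 swab and is to be compared with historical controls (19.1). But 19.2.2 applies it to the primary test, whose null value and n = 10 are those of the Phase IIa component. Nor does right-censoring above Ct 40 help: it covers values measured as non-detectable, not a visit that was never scheduled.

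**Conclusion.** The concern holds. The primary statistic as printed needs a Day 30 Ct that Phase IIa patients are not scheduled to give, and it contradicts both the sentence before it and the endpoint in 19.1. The values 130, 144 and 0.80 cannot be reconciled with either window. The most serious consequence is that the single-arm test against 130 could declare efficacy with no treatment effect.

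The textual conflict and the misfit of 130 rest on figures in the plan alone. The Days 0–14 power rests on the SDs and correlation of 19.3, no censoring (as 19.3 itself assumes), and the 14-unit difference taken at face value. The Days 0–30 figures also assume an SD and correlation at Day 30 that the plan does not give. This must be corrected before the primary analysis.

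**What to change.** In 19.2.2, set m = 4 and t = (0, 3, 7, 14), giving c = (1.5, 3.5, 5.5, 3.5). This matches 19.1 and the Main Cohort schedule. In 19.3, state which days and weights the pilot calculation used, then re-derive the null value, the alternative and the power from the pilot data on Days 0–14 with those weights, and name the window. Report any Day 0–30 AUC for the Expansion Cohort as a separate supportive analysis.

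If a Day 0–30 primary window was intended, a Day 30 swab has to be added for the Main Cohort in 11.2, 11.4 and its calendar, the endpoint text in 1.1, 8.1, 16.1 and 19.1 must change to match, and the SD roughly doubles under the assumptions above.

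The text change is short, uses existing pilot data and needs no new visits. The statistical cost is larger. With n = 10 the sponsor must accept a detectable difference of about 39.5 units, nearly three times the planned 14. Keeping 14 at 80% power would need about 70 patients under the stated SDs and correlation.
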